5.4.5 Management of neutropenia, leukopenia and thrombocytopenia

Adverse events of neutropenia and leukopenia should be managed as deemed appropriate by the Investigator with close follow up and interruption of study drug if CTCAE Grade 3 or higher occurs. For toxicity of Grades 1-2, especially if more than one toxicity is present, drug can be interrupted at Investigator discretion. Interruption can be up to a maximum of 4 weeks. Appropriate supportive treatment and causality should be considered. For CTCAE grade 3-4 toxicities, dose interruption until recovered to grade 1 or 2 or better (up to a maximum of 4 weeks) should be done. If repeat occurrences, then dose reduce olaparib to dose level -1 and AZD6738 to dose level -1 (hematologic) per above. If a second event happens, dose reduction of olaparib to dose level -2 and AZD6738 to dose level -2 should be done. If either dose does not have another dose level below, they should be removed from study.

G-CSF should be given according to local hospital guidelines for febrile neutropenia but not within 24 hours of the last dose of study treatment unless absolutely necessary. Primary prophylaxis with G-CSF is not allowed. After G-CSF, treatment can resume at the earliest 24 hours after last G-CSF dose OR 7 days for pegylated G-CSF.

For cases where patients develop prolonged hematological toxicity (>2-week interruption/delay in study treatment due to CTCAE Grade 3 or worse), refer to Section 5.4.14.

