5.4 Management of Toxicity

5.4.1 Toxicities that require discontinuation from protocol therapy

Any toxicity observed during the course of the study should be managed in the first instance by interruption of the dose of study treatment and dose reductions if necessary. Repeat dose interruptions are allowed as required for a maximum of 28 days on each occasion. Treatment must be interrupted until the patient recovers completely or the toxicity reverts to NCI CTCAE grade 1 or 2 (depending on toxicity) or to the baseline CTCAE grade. If the required interruption is any longer than 28 days due to toxicity, the patient must be removed from the study. If at any point during study treatment, it becomes apparent that the tumor is not coming under control, patients are to be removed from study and treated as clinically indicated.

Protocol therapy should be discontinued if a patient experiences:

- Any CTCAE Grade 4 toxicity with the exception of:
 - CTCAE Grade 4 neutropenia of 5 days or fewer duration
 - CTCAE Grade 4 nausea, vomiting or diarrhea that resolves to Grade 3 in less than 72 hours in patients who have not received optimal anti-emetic or anti-diarrheal therapy
 - CTCAE Grade 4 laboratory abnormalities that can be readily corrected within 72 hours and do not result in hospitalization
- CTCAE Grade 3 or 4 thrombocytopenia with bleeding requiring hospitalization

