Treatment is delayed to allow resolution to asymptomatic Grade 2, Grade 1 or lower (up to 28 days maximum). Transfusions may be done at provider's discretion. Upon recovery, olaparib is reduced by one dose level (if possible).

1. AZD6738 is moved down one dose level. Either from dose level 0 to dose level -1 (hematologic toxicity, which is 160 mg daily Days 1-4) OR from dose level -1 (hematologic or non-hematologic) to dose level -2.

Third episode:

5. Symptomatic Grade 2 or Grade 3:

A treatment delay up to 28 days maximum (with or without transfusion) to allow resolution to asymptomatic Grade 2, Grade 1 or lower. Upon recovery, Olaparib is dose reduced by one level (if possible).

1. AZD6738 is moved down one dose level to dose level -2 (if possible).

If no further reductions are possible because olaparib or AZD6738 are already at dose level -2, the patient should be removed from the study.

Fourth episode:

6. Symptomatic Grade 2: Patient is removed from study
7. Grade 3: Patient is removed from study

Any episode of Symptomatic Grade 2 or Grade 3 anemia in conjunction with Grade 2 or higher neutropenia, leukopenia or thrombocytopenia

Treatment is delayed to allow resolution of anemia to asymptomatic Grade 2, Grade 1 or lower and thrombocytopenia/leukopenia/neutropenia to Grade 2 or lower (up to 28 days maximum). Provider may do transfusions at their discretion. Upon resumption of therapy, olaparib is dose reduced by one level. AZD6738 is dose reduced by one dose level. Either from dose level 0 to dose level -1 (hematologic toxicity, which is 160 mg daily Days 1-4) OR from dose level -1 (hematologic or non-hematologic) to dose level -2.

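### Sections 5.4.5 and 5.4.4 direct hold-and-recover for severe cytopenias without excluding the events that end therapy under 5.4.1

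*Combined protocol and SAP*

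**What the plan says.** Section 5.4.1 begins by saying that any toxicity "should be managed in the first instance by interruption of the dose of study treatment", with dose reduction if needed. It then lists what ends protocol therapy. The first trigger is "Any CTCAE Grade 4 toxicity with the exception of" three items, two of which bear on blood counts: "CTCAE Grade 4 neutropenia of 5 days or fewer duration" and "CTCAE Grade 4 laboratory abnormalities that can be readily corrected within 72 hours and do not result in hospitalization". A separate trigger is "CTCAE Grade 3 or 4 thrombocytopenia with bleeding requiring hospitalization".

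Section 5.4.5 covers neutropenia, leukopenia and thrombocytopenia. Its instruction is "For CTCAE grade 3-4 toxicities, dose interruption until recovered to grade 1 or 2 or better", for no more than 4 weeks. Recurrence moves both drugs to level -1 and then level -2, and a patient with no lower level left comes off study.

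The last paragraph of Section 5.4.4 applies to "Any episode of Symptomatic Grade 2 or Grade 3 anemia in conjunction with Grade 2 or higher neutropenia, leukopenia or thrombocytopenia". Treatment is delayed for up to 28 days until the anemia has improved and the other counts are at Grade 2 or lower. Then: "Upon resumption of therapy, olaparib is dose reduced by one level", and AZD6738 also drops one level.

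Neither 5.4.5 nor that paragraph mentions 5.4.1 or sets aside the events listed there.

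Section 10.3.4 first defines excessive toxicity as a removal that happens even though the dose had been modified. Its next sentence sets the 25% limit on subjects who must stop because of toxicity, with no condition about dose modification.

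**The concern.** The grade ranges in 5.4.5 (3-4) and 5.4.4 (2 or higher) take in events for which 5.4.1 allows no return to treatment. Read alone, either section appears to cover those events in full: hold, wait for recovery, go on at the same or a lower dose. Section 1.1.2 names neutropenia and thrombocytopenia as the main dose-limiting toxicities, and 5.4.3 expects hematologic toxicity to be the biggest challenge, so these are the sections that sites will consult most.

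What is at stake is re-exposure after a severe marrow event. Study drug is held at onset under every section, so the risk arises only at the decision to restart. The lead site's ongoing review of adverse event and laboratory data (9.6) and the quarterly review (7.3) could catch an improper restart, but possibly only after it has happened.

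A second question arises in 10.3.4. An immediate removal under 5.4.1 may involve no earlier dose modification, and on the literal definition it might be left out of the toxicity count.

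**Working it through.** The plan states no figure on this point, so the check sets the rules side by side.

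**Event by event**

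| Event | 5.4.1 | 5.4.5 read alone | 5.4.4 last paragraph read alone (if with qualifying anemia) |
|---|---|---|---|
| Grade 4 neutropenia, more than 5 days | End therapy | Hold until recovery | Delay, then reduced doses |
| Grade 4 leukopenia or thrombocytopenia, not readily corrected within 72 hours or leading to hospitalization | End therapy | Hold until recovery | Delay, then reduced doses |
| Grade 3-4 thrombocytopenia with bleeding needing hospitalization | End therapy | Hold until recovery | Delay, then reduced doses |
| Grade 4 neutropenia, 5 days or fewer | Exempt | Hold until recovery | Delay, then reduced doses |

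The first three rows differ and the fourth does not. The laboratory exception cannot rescue the first row, because more than 5 days is more than 5 × 24 = 120 hours, beyond its 72-hour limit.

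**Is restart actually stated?** In 5.4.4 it is, through the dose set for resumption. In 5.4.5 it is mostly implied by the recurrence rule, although the G-CSF paragraph does say when treatment may resume after G-CSF and attaches no limit on how long the neutropenia lasted.

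**Do other sections close the gap?**
- Section 5.4.14 discontinues treatment only if counts have not recovered to Grade 1 or better within 4 weeks.
- Section 5.4.3 requires an ANC of at least 1000/µL and platelets of at least 75,000/µL to start a cycle.
- Take a hypothetical patient with Grade 4 neutropenia for 8 days, who is back to Grade 1 by day 20 with adequate platelets. He passes both checks, since 5.4.14 places Grade 3 or worse at an ANC below 1 × 10⁹/L. Only 5.4.1 takes him off therapy.
- Section 5.4.6 restates the Grade 4 stop, but for non-hematologic toxicity only. Sections 5.4.8 and 5.4.9 send the reader to 5.4.6 for it. For stopping or work-up, 5.4.5 refers only to 5.4.14.

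**Restarts allowed, worst case, from dose level 0**
- 5.4.1: 0.
- 5.4.5 read literally: 3. The first restart is at level 0 (no reduction is stated for a first event), the next at level -1, the next at level -2; a further event means removal.
- 5.4.4 last paragraph: 2. One restart at level -1 and one at level -2, then removal under that section's note on level -2.

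These counts need the same patient to have repeated events of this severity and to recover in time on each occasion. The 5.4.5 count also takes its second event to come after the repeat occurrence, which the wording leaves open.

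**Section 10.3.4.** Monitoring starts at 10 subjects, with a halt above 25%. At n = 10, 2/10 = 20% does not halt and 3/10 = 30% does. At the planned total of 47 (35 + 12), 11/47 = 23.4% does not halt and 12/47 = 25.5% does. Near the limit, whether one immediate removal counts can decide the outcome.

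**The case against.** The strongest reply is that this is a missing cross-reference and not a contradiction. Section 5.4.1 carries discontinuation in its title, opens the toxicity section and speaks of blood counts directly. Its 5-day neutropenia limit would do no work unless it overrode 5.4.5. The sections can also be read in sequence: interruption comes first under 5.4.1 too, and whether neutropenia outlasts 5 days is known only while drug is being held. The grade range in 5.4.5 keeps a meaning on this reading, since it covers Grade 3 and the exempt Grade 4 events. The resumption sentence in 5.4.4 can be taken to set the dose if therapy resumes. Section 5.4.6 itself pairs a Grade 4 stop with later language on resuming after Grade 3 or 4 toxicity.

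Most of this stands, and it is why 5.4.1 should be taken to control. What it does not supply is a statement of that precedence for blood counts. The protocol supplies one for non-hematologic toxicity, which makes its absence in 5.4.5 easier to misread.

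On 10.3.4, a reader might infer that immediate removals are certainly left out of the 25% rule. The text does not support that, because the sentence that sets the limit, and the one on monitoring withdrawals, carry no dose-modification condition. The fair description is an ambiguity within the section.

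**Conclusion.** The point holds as a gap in the safety instructions that should be fixed. Three classes of blood-count event that end therapy under 5.4.1 fall within the hold-and-recover instructions of 5.4.5 and the last paragraph of 5.4.4, and no text says which governs.

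A reader might go further and infer that the protocol orders re-treatment of these patients, or that several restarts are to be expected. The documents support neither. 5.4.1 is the better controlling reading, and the three and two restarts are worst cases. The documents give no rate for these events, so neither the number of patients affected nor the effect on the 25% rule can be derived.

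Nor does the point reach the efficacy analysis. Section 10.2.1 keeps every eligible patient who received at least one dose in the response analysis, so the response denominators are unaffected.

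The conclusion assumes that the 72-hour laboratory exception applies to leukocyte and platelet counts. If it does not, 5.4.1 ends therapy for every Grade 4 leukopenia or thrombocytopenia and the overlap is wider.

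**What to change.** Add *except events requiring discontinuation under Section 5.4.1* in two places: the Grade 3-4 sentence of 5.4.5 and the combined-cytopenia paragraph of 5.4.4.

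Separately, state in 10.3.4 that every removal from treatment for toxicity counts toward the 25% limit, including immediate removals under 5.4.1 with no prior dose modification.

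The cost is one clause in two places and one sentence, with no new data collection. The downside is that some patients whose counts recover cannot restart, which 5.4.1 already intends, and that the 25% limit may be reached slightly sooner.

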5.4.2 Dose levels for olaparib and AZD6738

Both drugs have two levels allowed for dose reductions and may be dose reduced stepwise per instructions below. Once a dose is reduced, escalation is not permitted. All dose modification and interruptions (including any missed doses) and the reasons for the modifications/interruptions are to be recorded in the eCRF. Repeat dose interruptions are allowed as required, for a maximum of 4 weeks on each occasion.

AZD6738 has a unique aspect in that its hematologic toxicity (specifically neutropenia, leukopenia, thrombocytopenia, see section 5.4.5) is schedule rather than dose-dependent. For hematologic toxicities related to AZD6738 requiring a single dose reduction, the schedule is adjusted rather than the daily dose (see Table 1). Non-hematologic toxicities requiring dose reductions (as both drugs would be lowered by one level), daily dose is lowered rather than schedule. If both a hematologic (related to AZD6738 per 5.4.5) AND non-hematologic Grade 3+ toxicity requiring dose reduction occur concurrently, both drugs are dose reduced. Olaparib is reduced by one dose level, while if AZD6738 is on dose level 0 is reduced to dose level -2 at first reduction.

TABLE 1 Dose Modification Table for AZD6738

Dose Level	AZD6738
0	160 mg daily Days 1-7
-1 (Hematologic toxicity)	160 mg daily Days 1-4
-1 (Non-hematologic toxicity)	120 mg daily Days 1-7
-2	120 mg daily Days 1-4

TABLE 2 Dose Modification Table for Olaparib

Dose Level	Olaparib
0	300 mg BID Days 1-28
-1	250 mg BID Days 1-28
-2	200 mg BID Days 1-28

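### Section 5.4.5 gives fixed dose levels for repeat Grade 3-4 cytopenia and does not cover a patient already at level -1; read literally, it conflicts with the stepwise, no-escalation rule in 5.4.2

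*Combined protocol and SAP*

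**What the plan says.** Section 5.4.5 handles Grade 3-4 neutropenia, leukopenia and thrombocytopenia first by interruption until recovery. It then says: "If repeat occurrences, then dose reduce olaparib to dose level -1 and AZD6738 to dose level -1 (hematologic) per above". The next sentence reads: "If a second event happens, dose reduction of olaparib to dose level -2 and AZD6738 to dose level -2 should be done". The paragraph closes with a removal clause: "If either dose does not have another dose level below, they should be removed from study".

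Table 1 in 5.4.2 has two different AZD6738 levels numbered -1. The hematologic one is "160 mg daily Days 1-4" and the non-hematologic one is "120 mg daily Days 1-7". Level -2 is "120 mg daily Days 1-4". The text of 5.4.2 describes reductions as stepwise and adds: "Once a dose is reduced, escalation is not permitted". It also says that a single reduction for AZD6738-related hematologic toxicity alters the schedule and not the daily dose, and that a non-hematologic reduction lowers both drugs by one level.

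Section 5.4.4 includes a rule for anemia occurring together with Grade 2 or higher neutropenia, leukopenia or thrombocytopenia. There each drug goes down one level. For AZD6738 this means from 0 to -1 (hematologic), "OR from dose level -1 (hematologic or non-hematologic) to dose level -2".

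**The concern.** A fixed landing level works without difficulty only when both drugs are still at level 0. The qualifier in 5.4.5 picks out one of the two -1 levels, so for a patient on the other one the instruction is a sideways move. That move raises the daily dose which a non-hematologic toxicity had caused to be lowered. For a patient already on the named level, the instruction changes nothing.

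These starting points can be reached by following the protocol. Section 5.4.6, with 5.4.2, takes both drugs to -1 (non-hematologic for AZD6738). The anemia-with-cytopenia rule in 5.4.4 takes both to -1 (hematologic for AZD6738). Section 5.4.3 expects hematologic toxicity to be the main difficulty, and section 1.1.2 names neutropenia and thrombocytopenia as the principal dose-limiting toxicities, so this paragraph is likely to be used. The synopsis plans four centers, and two of them could give the same patient different doses while each believed it was following the protocol.

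**Working it through.** The plan states no cycle totals, so there is no figure to reproduce. The inputs are Tables 1 and 2 in 5.4.2.

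**Dose per 28-day cycle** (daily dose x dosing days)

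| Level | AZD6738 | Olaparib |
|---|---|---|
| 0 | 160 x 7 = 1,120 mg | 300 x 2 x 28 = 16,800 mg |
| -1 (hematologic) | 160 x 4 = 640 mg | 250 x 2 x 28 = 14,000 mg |
| -1 (non-hematologic) | 120 x 7 = 840 mg | 250 x 2 x 28 = 14,000 mg |
| -2 | 120 x 4 = 480 mg | 200 x 2 x 28 = 11,200 mg |

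Table 2 has only one olaparib level -1, so it appears in both -1 rows.

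**Literal 5.4.5 target (AZD6738 -1 hematologic, olaparib -1) applied to three starting points**

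| Start: AZD6738 / olaparib | AZD6738 daily dose | AZD6738 per cycle | Olaparib |
|---|---|---|---|
| 0 / 0 | 160 to 160 mg, no change | 1,120 to 640 mg | 300 to 250 mg BID |
| -1 (non-hematologic) / -1 | 120 to 160 mg: 160/120 - 1 = +33.3% | 840 to 640 mg: 640/840 - 1 = -23.8% | 250 mg BID, no change |
| -1 (hematologic) / -1 | 160 mg, no change | 640 mg, no change | 250 mg BID, no change |

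The first row behaves as a reduction should. The second row sets 5.4.5 against two statements in 5.4.2: that a reduced dose is not raised again, and that hematologic toxicity alters the schedule and leaves the daily dose alone. The third row is a reduction that reduces nothing. The removal clause resolves neither the second nor the third row, because level -2 still lies below both drugs.

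**Size of the difference from the 5.4.4 wording.** The anemia-with-cytopenia rule would take the second-row patient to level -2 for both drugs. The AZD6738 daily dose stays at 120 mg, the cycle total goes from 840 to 480 mg (480/840 - 1 = -42.9%), and olaparib goes from 250 to 200 mg BID (-20%). This measures how far the two sections diverge and does not favor either.

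**Counting events.** A repeat occurrence leads to -1 and a second event leads to -2, but the second Grade 3-4 episode can be described as either. For a patient starting at level 0, the two readings give AZD6738 640 or 480 mg per cycle and olaparib 250 or 200 mg BID.

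**The case against.** The strongest reply is that 5.4.2 governs. It makes reductions stepwise and forbids escalation, while 5.4.5 speaks of reducing, refers back to what precedes it, and ties removal to whether a lower level exists. A careful investigator would probably infer a stepwise intent. That stands as a reading of intent, and it rules out the stronger inference that the protocol orders a dose increase. It does not supply an instruction: 5.4.5 names a specific level, and nothing says which sentence yields when the two collide.

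A reader might also infer that the literal rule restores a dose the patient had shown he could not tolerate. The documents do not establish this. Non-hematologic reductions lower both drugs together, so the earlier toxicity need not have been due to AZD6738. The cycle total falls by 24%, and 5.4.2 describes these cytopenias as depending on AZD6738's schedule more than on its dose.

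Nor does 5.4.4 show which rule is right. It covers anemia, alone or with another cytopenia, and the protocol gives a separate rationale for anemia, attributing it mainly to olaparib. Different toxicities may have different rules. A patient at olaparib -1 after a first Grade 3 anemia normally still has AZD6738 at level 0, so 5.4.5 does reduce one drug; the absence of an olaparib step is not in itself an error. Section 5.4.2 does consider hematologic and non-hematologic toxicity occurring concurrently and sends AZD6738 from 0 to -2, but it does not cover the two in sequence.

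A further tempting inference is that this would affect the 25% toxicity-withdrawal rule in 10.3.4. Even the direction is unsettled: the literal text keeps the patient at -1, whereas a one-level step brings him sooner to -2, where the next required reduction means removal. No frequency is given from which to estimate an effect.

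On event counting, the natural sequence is interrupt, then -1, then -2, then removal. That is probably what is meant, so the ambiguity is minor.

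**Conclusion.** The point holds as an internal contradiction in a dosing rule. Section 5.4.5 sets fixed landing levels, does not address a drug already at -1, and read literally conflicts with 5.4.2. For a patient at AZD6738 -1 (non-hematologic) and olaparib -1, the literal result is a daily dose 33% higher, a cycle total 24% lower, and no olaparib change. For a patient at -1 (hematologic) and olaparib -1, neither drug changes.

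This assumes that olaparib is at -1 when AZD6738 is. That is the usual case after a non-hematologic reduction, because both drugs are lowered together; with olaparib already at -2, the removal clause could apply instead. The scope is also limited: 5.4.1 stops treatment for some Grade 4 events, so Grade 3 events and brief Grade 4 neutropenia are the main cases. How often these sequences would arise cannot be derived from the documents. No sample size, power or type I error figure depends on this point. The unnumbered events are a lesser drafting fault in the same paragraph.

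**What to change.** The sponsor should reconcile 5.4.2, 5.4.4 and 5.4.5. Section 5.4.5 should number its events, as 5.4.4 numbers its episodes, and give one action for each event at each possible starting level. That includes AZD6738 already at -1 (non-hematologic), AZD6738 already at -1 (hematologic), and olaparib already at -1. If 5.4.5 is meant to differ from the anemia-with-cytopenia rule, or to take precedence over the no-escalation sentence, it should say so. Which rule or dose applies is for the sponsor to decide.

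The cost is the rewording of one paragraph in an amendment, with cross-references checked. It needs no new procedures, data or patients.

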5.4.6 Management of non-hematologic toxicity

Acute toxicities should be managed as medically indicated, with temporary suspension of IP and initiation of supportive care as clinically indicated by the treating physician. Treatment and study participation must be stopped for Grade 4 non-hematologic toxicity excluding; a) Grade 4 nausea, vomiting, diarrhea that resolves to Grade 3 in less than 72 hours in patients who have not received optimal anti-emetic or anti-diarrheal therapy and b) Grade 4 laboratory abnormalities that can be readily corrected within 72 hours and do not result in hospitalization. At the first occurrence of CTCAE grade 3 or 4 non-hematologic toxicity that resolves to CTCAE grade 1 or 2 with supportive measures and treatment hold under 28 days, treatment may be resumed. At the resolution of the first occurrence of a toxicity, a change to dose is not automatically required unless indicated by the specific nature of the AE in severity or recurrence in view of provider. At the second occurrence, upon resolution of toxicity, it is suggested that olaparib AND AZD6738 should be dose reduced by one dose level (if possible). If no dose reduction is possible (e.g. either drug already at dose level -2), the patient is removed from study. If the required interruption is longer than 28 days due to toxicity, the patient must be removed from the study treatment unless approved by the Principal Investigator.

